5.3 Endpoint(s)

5.3.1 Primary Endpoint(s)

The bacterial colonization rate at the CVC tip and the catheterization site on the skin after removal (number of culture-positive cases/total catheters × 100%)

The primary endpoint is the removal of the CVC from the patient with deep vein catheterization to perform catheter-tip culture and sampling and culture of bacteria from the skin around the insertion site.

5.3.2 Secondary Endpoint(s)

Removal of other types of DVCs, such as hemodialysis and PICCO to perform catheter-tip culture and sampling and culture of bacteria from skin around the insertion site;

Occurrence of suspected CLABSI/CRBSI, performing catheter-tip culture and blood bacterial culture;

Dressing securement performance, such as lift or drop-off;

Safety indicators, mainly referring to the effect of the dressing on the state of the skin.

6.0 POPULATION AND DURATION

The study will include 440 study subjects. The study will be conducted simultaneously in two ICU wards of Shanghai Ruijin Hospital.

The overall study is expected to last a total of 15 months. Depending on the subject's disease condition and treatment schedule, each subject's treatment duration with the same deep vein catheter is essentially no more than 2 weeks, so their participation in the study will last for approximately 3-14 days.

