4.1.2 Minimization of Bias

The following measures have been taken to minimize or avoid bias in this study:

- **Randomization:** The random assignment gives each subject an equal chance of being assigned to either the test or control group without being influenced by the subjective intention of the investigator and/or the subject, allowing for a balanced distribution of multiple influence factors and avoiding selection bias or information bias as much as possible. This trial will use a random assignment approach to reduce bias due to sampling difference. After investigators confirm and verify the inclusion and exclusion criteria, eligible subjects will be randomly assigned to either the test group or the control group to receive treatment. The random number table is generated by a biostatistician using a program before the first enrollment.
- **Parallel-group control:** A parallel-group controlled approach is used in the trial design. Treatment of both test and control groups will be conducted concurrently so that factors that may affect the validity assessment are evenly distributed between the two groups.

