10.2.1 Randomization

Subjects will be randomly assigned to either the test or control group using an online randomization service by a 1:1 assignment ratio.

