3.3 Randomization

After investigators confirm checks of inclusion and exclusion criteria, eligible participants were given a randomization number through the online randomization service system and randomly assigned to either the trial or control group to receive trial treatment in a 1:1 grouping ratio. The random number table was generated by a biostatistician using a program prior to enrollment of the first participant and then imported into the online randomization service system. See the randomization scheme for details.

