6.3 Efficacy Evaluation

6.3.1 Primary Efficacy Evaluation

(1) Evaluation Indicators

Occurrence rate of bacterial colonization of the CVC tip segment and skin at the insertion site after extubation (number of culture-positive cases/total catheters × 100%)

Primary endpoint: Positive rates of catheter tip cultures and sampling cultures of skin surrouding the insertion site in patients with deep vein indwelling catheterization after CVC tubes were removed.

(2) Evaluation method

FAS and PPS were used for both total catheter count and participant level evaluation. If more than one catheter of the same type was available for the same participant and the culture results were inconsistent, a positive culture result was taken for that participant when participant-level analysis was performed.

Describe the number and percentage of cases of bacterial colonization of the CVC tip segment and skin at the insertion site after extubation in both groups, and compare the two groups using a chi-square test or Fisher's exact test.

In addition, because some subject may have two or more than two CVC, which are interrelated, a generalized mixed linear model was developed to evaluate the difference in the occurrence rate of bacterial colonization between the two groups, using the occurrence rate of bacterial colonization of the CVC tip segment after extubation and the occurrence rate of bacterial colonization of the skin at the CVC insertion site after extubation as dependent variables, group as a fixed effect, and insertion site, skin infection of baseline insertion site, and their interaction as random effects, respectively.

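### Two ICU wards recruit, but ward is not a stated stratification factor, a listed baseline item or an analysis term: a small, free gain in precision is left unused

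*Protocol*

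**What the plan says.** **Setting.** Protocol 6.0: "The study will be conducted simultaneously in two ICU wards" of one hospital.

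**Randomisation.** Protocol 10.2.1: "Subjects will be randomly assigned to either the test or control group using an online randomization service by a 1:1 assignment ratio". Protocol 4.1.2 adds: "The random number table is generated by a biostatistician using a program before the first enrollment". SAP 3.3 repeats the 1:1 ratio and the pre-generated table, names no stratification factor, and ends: "See the randomization scheme for details". That scheme is a separate document and was not supplied.

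**Baseline data.** Ward is not among the items in Protocol 10.2.2 or SAP 6.2.2.

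**Analysis.** For the primary endpoint, SAP 6.3.1 says to "compare the two groups using a chi-square test or Fisher's exact test", at catheter level and at participant level. It adds a mixed model with "group as a fixed effect, and insertion site, skin infection of baseline insertion site, and their interaction as random effects". SAP 6.3.2 uses the same model structure for the rate per 1,000 catheter-days, and chi-square, Fisher, t or rank-sum tests elsewhere. Protocol 19.4 is in line with this. None of these analyses contains ward.

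**The concern.** The endpoint is a culture result that depends on how the catheter and site are handled, and ward is a known recruitment unit. If the wards differ in colonisation rate, an uneven split of one ward between the arms moves the observed difference in that trial. The plan as written neither states that it prevents such a split nor adjusts for it, and it has no table that would reveal one.

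There is a second route. If the unsupplied scheme does stratify by ward, the analysis does not reflect the design. The test's variance then still contains the between-ward component that the allocation has removed from the estimate.

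At stake are a little power, the credibility of the estimate if the wards turn out unevenly split, and a simple check that the result is similar in both wards. Adjustment chosen after open-label results are known would carry less weight than adjustment written down beforehand.

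**Working it through.** **Inputs from the documents.** Control rate 18.7%, 50% relative reduction (so 9.35% in the test arm, a difference of 9.35 points), 220 per arm, 80% power, two-sided 5% (Protocol 19.2, SAP 3.2). Final-analysis threshold 0.048 (SAP 6.1).

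**Assumptions, because the documents give no ward figures.** Control-arm ward gaps of 0, 10 and 20 points around 18.7%; ward sizes 50:50 or 70:30; the 50% relative reduction holds in each ward.

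**1. The plan's own sample size.** With mean rate (0.187 + 0.0935)/2 = 0.14025:

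n = [1.960 × √(2 × 0.14025 × 0.85975) + 0.8416 × √(0.187 × 0.813 + 0.0935 × 0.9065)]² / 0.0935² = (0.9625 + 0.4095)² / 0.00874 ≈ 216 per arm.

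At 0.048 it is 219. Both agree with the stated 220, without a continuity correction. (With the correction that the text seems to name, it would be 237. That is a separate matter and does not affect the comparison below.)

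**2. Size of a chance ward imbalance under simple 1:1 allocation.** The SD of the difference in ward share between arms is √(2 × s(1 − s)/220).
- 50:50 wards: √(2 × 0.25/220) = 4.77 points; 1.96 × 4.77 = 9.3 points.
- 70:30 wards: √(2 × 0.21/220) = 4.37 points; 1.96 × 4.37 = 8.6 points.

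**3. Effect on the estimate in one trial.** The shift equals the share difference times the average ward gap over the two arms. With no treatment effect the gap is the same in both arms. With a 50% reduction it halves in the test arm, so the average is 0.75 of the control-arm gap.

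| Control-arm gap | No treatment effect | 50% reduction |
|---|---|---|
| 10 points | 9.3 × 0.10 = 0.9; 8.6 × 0.10 = 0.9 | 9.3 × 0.075 = 0.7; 8.6 × 0.075 = 0.6 |
| 20 points | 9.3 × 0.20 = 1.9; 8.6 × 0.20 = 1.7 | 9.3 × 0.15 = 1.4; 8.6 × 0.15 = 1.3 |

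Entries are points, for 50:50 then 70:30 wards, at the 95% limit of imbalance. The standard error of the risk difference is √(2 × 0.187 × 0.813/220) = 3.7 points with no effect and √((0.1520 + 0.0848)/220) = 3.3 points under the alternative. Even the largest shift is about half a standard error (1.9/3.7).

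**4. Operating characteristics by simulation** (100,000 trials per scenario, 440 patients, two-sided 0.05, simple allocation, 50:50 wards):

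| Gap | Type I error: chi-square | Type I error: ward-stratified CMH | Power: chi-square | Power: CMH |
|---|---|---|---|---|
| 0 | 0.050 | 0.050 | 0.816 | 0.814 |
| 10 | 0.050 | 0.050 | 0.818 | 0.820 |
| 20 | 0.049 | 0.050 | 0.818 | 0.834 |

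The mean estimated difference was 0.000 with no effect and 0.093 to 0.094 under the alternative, so there is no systematic bias. At the SAP's 0.048 level the planned test has type I error of about 0.048 to 0.050. CMH power is then equal with no gap (0.81 v 0.81) and higher by about 0.4 to 1.8 points at gaps of 10 to 20 points. The 0.2-point deficit at 0.05 with no gap is absent at 0.048.

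**5. If the list is in fact stratified by ward.** For equal wards the between-ward share of variance is (gap/2)²/(0.187 × 0.813): 0.0025/0.152 = 1.6% at 10 points and 0.01/0.152 = 6.6% at 20 points. The unadjusted test then behaves as if its critical value were 1.96/√(1 − 0.016) = 1.976 or 1.96/√(1 − 0.066) = 2.028. That is a real type I error of 0.048 or 0.043 against a nominal 0.05. Simulation at 0.05 gives about 0.048, and 0.041 to 0.044. At 0.048 it gives about 0.042 to 0.047 for the unadjusted chi-square and about 0.047 to 0.049 for CMH.

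**The case against.** The case for leaving the plan alone is strong on several counts.

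- **Validity.** Patients, not wards, are randomised, and chance imbalance in an unadjusted covariate is already in the standard error. This stands. A reader might infer that ward differences go uncontrolled, or that they bias the comparison. The documents do not support that: the allocation is individual and concurrent, and the planned test keeps its error rate and is unbiased on average even at an assumed 20-point gap.
- **Separate nursing teams.** A reader might also infer that each ward has its own nurses and its own dressing or sampling practice. No section says so. The synopsis places patients in one critical care department, and Protocol 3.2 and 10.2.2 refer to the hospital's standard and to departmental procedures. Nothing shows that the wards differ in colonisation.
- **The missing scheme.** The randomisation scheme may already stratify by ward, so absence of stratification cannot be asserted. This stands too, but it does not close the point. If the scheme stratifies, the analysis should reflect it; if it does not, the analysis is the remaining place to use ward.
- **The primary test.** CMH departs from the Z test used for the sample size, and it does not handle several CVCs in one patient. The second part limits the change to the participant-level comparison. The first has little practical weight, since power at 220 per arm is no lower at 0.048.
- **Size.** The gain is small and rests on assumed ward gaps. Agreed.

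**Conclusion.** The gap is real and small. Ward is not a stated stratification factor, a listed baseline variable or a term in any efficacy analysis. The planned comparison stays valid and unbiased on average, and the required sample size does not change materially.

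The cost of omitting ward is about 0.4 to 1.8 points of power at assumed ward gaps of 10 to 20 points, and nothing if the wards do not differ. In a trial with an imbalance at the 95% limit, the estimate moves by 0.6 to 1.4 points under the planned effect, against a standard error of 3.3. If the list is ward-stratified, the unadjusted chi-square runs at about 0.042 to 0.047 instead of 0.048, which is conservative, not anti-conservative.

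All of these sizes rest on the assumed ward rates and ward sizes. The point is a free improvement in precision and reporting, not an error that threatens the trial's conclusion.

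**What to change.** 1. State in SAP 3.3 whether the randomisation scheme stratifies by ward. If it does not and the list is not yet in use, stratify it by ward.
2. Record ward at randomisation as a baseline item (Protocol 10.2.2, SAP 6.2.2).
3. In SAP 6.3.1, make the participant-level primary comparison a Cochran-Mantel-Haenszel test stratified by ward, with the common risk difference and its confidence interval.
4. Add ward as a fixed effect in the mixed models of SAP 6.3.1 and 6.3.2, which serve the catheter-level analysis. Two levels are too few for a random effect.
5. Add one descriptive table of the primary endpoint by ward and arm.

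The cost is SAP wording, one recorded field and, if still possible, one stratum in the online system. No patients or visits are added. If recruitment has begun, items 2 to 5 can still be adopted, provided that they are fixed before outcomes are compared by arm.

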7.0 ENROLLMENT CRITERIA

Subjects enrolled in this clinical study must meet all the inclusion criteria and none of the exclusion criteria, as listed in the sections below.

7.1 Inclusion Criteria

Subjects may be included that meet the following criteria:

Table 7.1-1: Inclusion Criteria

| Number | Inclusion Criteria |
|--------|--|
| IC - 1 | The subject is 18 years old or older at the time of providing consent. |
| IC - 2 | The subject will be available to attend all visits required in the trial and have an expected length of stay in the ICU no less than 3 days. |
| IC - 3 | The subject or his/her legally authorized representative is competent to sign the informed consent form |
| IC - 4 | The patient must have a central venous catheter (CVC) used on him/her, which may or may not be used in combination with other types of DVCs |
| IC - 5 | The patient's catheter insertion site is free of deformities, phlebitis, infiltrations, dermatitis, eczema, rashes, breaks, burns, tattoos, or other skin conditions that could affect the integrity of the skin at the insertion site |
| IC - 6 | The patient will comply with the DVC treatment process and the nursing process prescribed in this protocol |

7.2 Exclusion Criteria

Subjects must be excluded from participating in this study if they meet any of the following criteria:

Table 7.2-1: Exclusion Criteria

| Number | Exclusion Criteria |
|---------|--|
| EC - 1 | The subject is unwilling/unable to attend the study visits. (Different from IC) |
| EC - 2 | There is sunburn, skin infections or scars, moles or other blemishes on the subject's catheter site that would affect the scoring or measurement of the test site |
| EC - 3 | The patient is assessed by the investigator as being at high risk of CLABSI, or known to be CLABSI, based on the environment, duration, and site conditions of catheterization |
| EC - 4 | The patient is documented or known to have allergies (sensitivities) to adhesive products, or other products involved in the trial, e.g. transparent dressings, CHG and alcohol |
| EC - 5 | The patient is being or has been subjected to other antibiotic, catheter or skin-related clinical trials |
| EC - 6 | The patient needs topical application of creams containing antimicrobial ingredients or other antimicrobial fluids beneath the Tegaderm CHG dressing or transparent dressing for skin disinfection, in addition to the requirements of this protocol |
| EC - 7 | The patient is assessed by the investigator as being at high risk of blood stream infection, or known to be sepsis, caused by blood stream infection |
| EC - 8 | The patient has dermatitis, burns, lesions, breaks, eczema, tattoos or other conditions at the catheter insertion site that would interfere with observation in the trial |
| EC - 9 | Women who are pregnant or breastfeeding |
| EC - 10 | Other patients deemed unsuitable for this trial by the investigator's judgment |

8.0 INFORMED CONSENT PROCESS

Informed Consent must be obtained for all subjects prior to any study activities being performed or data being collected. The Investigator or designee will review all relevant aspects of the study with the potential study subject that are relevant to the subject's decision to participate throughout the study. The Investigator or designee will provide ample time for

the subject to read and understand the IRB/EC approved Informed Consent Form and to consider participation in the study.

The study subject or legal authorized representative must sign and date the Informed Consent Form. The Investigator or designee must sign and date the Informed Consent Form. The Informed Consent Process must be documented by the Investigator or designee.

The Informed Consent Process includes documentation of the discussion regarding study procedures, subject concerns, that the subject was provided ample time to consider participation, and that all questions were answered prior to participation in any research activity.

The Investigator or designee must file the original Informed Consent Form and provide the subject with a copy of the signed and dated Informed Consent and any other written documentation per local IRB/EC requirements.

In order to minimize pressure and undue influence on vulnerable subjects, the Investigator or designee who is obtaining Informed Consent should ensure appropriate communication techniques, such as visual aids and avoidance of jargon, in order to ensure minimal pressure and undue influence is avoided.

9.0 POINT OF ENROLLMENT AND EXIT

9.1 Point of Enrollment

Following recruitment and eligibility screening, a subject will sign the informed consent form. A subject is considered enrolled in this study at time the Informed Consent process has been completed.

Eligible and consented subjects will be assigned a unique subject identification number, which will not contain information that could identify the subject.

9.2 Point of Exit

Study subjects may exit the study for a variety of reasons. The Investigator shall record the reason for withdrawal and discontinuation of the study in the applicable Case Report Form. These reasons include, but are not limited to:

- Study completion (all study related visit(s) are completed)
- Withdrawal by the Subject
- Withdrawal by Investigator
- Lost to follow-up
- Death
- Study Termination

If a subject withdraws or discontinues participation before study completion, the subject will not be accounted into the per protocol set (PPS) analysis until the required enrollment is reached but will be accounted into the safety set analysis.

[figure not shown]
Data collected until the last known contact of study subject may be used in the analysis of study data. Because the subjects in this study are all ICU patients, patients will be considered lost to follow-up if they are transferred out of the ICU or discharged without removal of the CVC. If the study subject withdraws from the study for any reason and there is an ongoing safety event, additional safety event information may need to be collected by the Investigator and shared with Sponsor.

10.0 PROCEDURES

The following sections describe the study procedures and data which will be collected at each procedure for the duration of the study. The data listed below, and any relevant safety data will be collected during this study.

10.1 Procedure Diagram

Signing of informed consent form, enrollment of subjects based on inclusion and exclusion criteria, etc.

10.2 Visits

After Informed Consent has been obtained, the following study procedures will be performed. All applicable data are to be recorded in the applicable Case Report Form (CRF).

10.2.1 Randomization

Subjects will be randomly assigned to either the test or control group using an online randomization service by a 1:1 assignment ratio.

10.2.2 Visit 1/Enrollment Visit/Baseline Visit (Study Day 0)

The following procedures will be completed at Visit 1:

1. Confirmation of subjects' eligibility and assessment of inclusion/exclusion criteria;
2. Randomization of patients who met the inclusion criteria;
3. Assessment of the skin condition around the catheter site.
4. Performing immediate dressing changes at all DVC insertion sites based on subjects' conditions at enrollment, using either the subject device 3M™ Tegaderm™ CHG I.V. Securement Dressing or the 3M™ Tegaderm™ Transparent Film Dressing as per randomization results, and following routine departmental nursing procedures;

The following data will be collected at the first visit:

1. Demographic information (height, weight, gender, age at consent);
2. Past medical history and allergic history, collected according to HIS records: Collection of medical and allergic history within the last 3 months related to the inclusion/exclusion criteria, including but not limited to diabetes, immune-related diseases, skin conditions, etc.;
3. Vital signs: Pulse, blood pressure, respiratory rate, body temperature;
4. Relevant laboratory tests, including blood routine examination: Red blood cell (RBC) count, white blood cell (WBC) count, neutrophil ratio, hemoglobin, platelets, C-reactive protein, etc.;

5. DVC type, site of insertion, duration, documentation of any post-puncture exudation, application of any other products such as gauze, hemostatic pads, etc.;
6. Documentation of skin conditions around the catheter site, scoring with reference to the standards for evaluating local skin irritation as listed in the appendix;
7. Medication use in relation to the trial, including mainly fat emulsions, heparin, blood transfusions and antimicrobial drugs;
8. Adverse events, device defects, complaints.

10.2.3 Follow-up visits (number of visits to be marked if there are multiple visits during each dressing change)

Since the expected use duration of the test/control product is a maximum of 7 days, there will be at least one visit on the seventh day into the trial (if catheterization duration is longer than 7 days), and more visits could be taken on a case-by-case basis. The following procedures will be completed at Follow-up visits:

1. Performing dressing changes in accordance with routine departmental nursing procedures;
2. Assessment of skin conditions around the catheter site, with reference to the standards for evaluating local skin irritation as listed in the appendix;

The following data will be collected during the follow-up visit:

1. Date and time of dressing change, site of dressing change, reason for dressing change. Scoring and assessment of edge curling in the case of dressing changes due to severely edge curling in the previous use;
2. Documentation of skin conditions around the catheter site, including erythema, edema, rash, etc., and scoring with reference to the standards for evaluating local skin irritation as listed in the appendix.
3. Any changes in medication use relevant to the trial, including mainly fat emulsions, heparin, blood transfusions and antimicrobial drugs;
4. Adverse events, device defects, complaints.

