3.0 STUDY DEVICE INFORMATION

Trial product

Working principle:

The primary purpose of 3M™ Tegaderm™ CHG I.V. Securement Dressing is to secure devices to skin; and secondly, the dressing contains an antimicrobial ingredient that inhibits microbial regeneration. This product is used to cover and protect the catheter sites on the body surface and to secure devices to skin and is available in a variety of models and sizes.

Product model: 1657R, 1658R, 1659R, 1660R

Size: 1657R, 8.5 cm x 11.5 cm (3-12 in x 4-1/2 in);

1658R, 10 cm x 12 cm (4 in x 4-3/4 in);

1659R, 10 cm x 15.5 cm (4 in x 6-1/8 in);

1660R, 7 cm x 8.5 cm (2 3/4 in. x 3 3/8 in)

The average CHG content (mg of CHG contained in the gel pad) of a single piece of dressing: 45 mg for both 1657R and 1658R; 78 mg for 1659R and 15 mg for 1660R.

Product usage

3M™ Tegaderm™ CHG Chlorhexidine Gluconate I.V. Securement Dressings is used to cover and protect catheter sites and to secure devices to skin.

Indications

The product is suitable for covering and protecting catheterization sites (covering arterial and venous catheters, intravascular catheters and percutaneous devices) on the body surface and securing the device to healthy skin. This product should not be used on infected wounds or unhealthy skins.

Contraindications

1. Do not use on patients with known hypersensitivity to chlorhexidine gluconate or alcohol;
2. Do not use at catheter insertion sites with dermatitis, burns, lesions or tattoos.

Warning

1. Use on infants with caution.
2. For external use only. Do not contact the product with ears, eyes, mouth or mucous membranes.

Precautions

1. The product shall not be used on broken wounds or unhealthy skin.
2. The product shall not be re-sterilized by gamma, electron beam or steam.
3. The skin must be dry and free of soap and hand sanitizer residue to prevent skin irritation and ensure good adhesion.

Possible adverse reactions associated with chlorhexidine gluconate

1. Occasionally, it can cause contact dermatitis. Highly concentrated solutions are highly

irritating to the eyes and conjunctiva.

2. Rare cases of local irritation and allergic reactions have been reported.
3. Children who accidentally eat it may develop symptoms of alcohol poisoning (e.g. slurred speech, drowsiness, wobbly gait, etc.) and there should be no delay in emergency medical treatment.

Control product

3M™ Tegaderm™ Transparent Film Dressing 1626W

Working principle

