The main purpose is to secure devices to skin.

Product features

Transparent dressing, i.e. CHG-free transparent dressing, can be used to cover and protect catheter sites on the body surface and to secure devices to skin, without any antibacterial ingredients, and are the currently most commonly used transparent dressings in DVC care in China.

Product usage

The product is used to cover and protect catheter sites on the body surface and to secure devices to skin.

Indications

It can be used to cover and protect catheter sites and wounds, maintain a moist environment, and also be used as a secondary dressing to cover those areas of skin susceptible to damage or abrasions or to secure devices.

Contraindications

There are no known contraindications.

Warning:

1. This product shall not be used as a substitute for sutures and other primary wound closures.
2. This product shall not be used on infected catheter sites or infected wounds.

Precautions

1. Apply dressing until bleeding has stopped.

2. The dressing shall not be stretched during application, as tension can cause skin trauma.
3. The skin must be dry and free of soap and hand sanitizer residue to prevent skin irritation and ensure good adhesion.
4. Dressings shall not be re-sterilized by gamma, electron beam or steam.
5. Antibacterial ointments containing polyethylene glycol may disrupt the strength of the film.
6. This dressing may be used on infected areas only under the care of a healthcare professional.

Table 3.0-1: Device Information

| Name of device | Model |
|--|----------------------------|
| 3M™ Tegaderm™ CHG I.V. Securement Dressing | 1657R, 1658R, 1659R, 1660R |
| 3M™ Tegaderm™ Transparent Dressing | 1626W |

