19.3 Population for Analyses

Full analysis set (FAS): The set of subjects determined according to the principle of Intention to Treat (ITT) refers to the data set composed by all subjects who are involved in the trial randomly and have used the trial product. The missing data were carried forward using the strategy of WCCF (Worst Case Care Forward) in case the primary efficacy endpoints of the patients were not observed. FAS is the primary analytical data set for evaluating validity.

Per protocol set (PPS): PPS is a subset of the FAS and includes subjects randomly assigned to treatment with a test or control device who have not experienced significant protocol deviations. The PPS is the secondary analytical data set for evaluating validity.

Safety analysis set (SS): This includes all subjects who have been formally enrolled and completed catheterization and dressing securement with the catheter in place for more than 24 hours. This data set is used to evaluate the safety of this trial.

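### Visit 1 lists the scored skin assessment after open-label randomisation, and the FAS omits randomised subjects who are never dressed, so baseline skin records and FAS membership can both be settled with the arm known

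*Protocol*

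**What the plan says.** Protocol 10.2.2 numbers the Visit 1 procedures:

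1. the eligibility check, including "assessment of inclusion/exclusion criteria";
2. random allocation of those who qualify;
3. "Assessment of the skin condition around the catheter site";
4. an immediate dressing change at every DVC site with the allocated product.

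Table 10.3-1 also puts the skin-assessment row below the randomisation row, within the same Day 0 column. Protocol 4.1.1 states that neither investigators nor subjects can be blinded. SAP 6.1 takes as baseline the last value before treatment, not before randomisation.

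Damaged insertion-site skin is an enrolment matter for everyone (IC-5, EC-2, EC-8), and Protocol 4.1.2 puts that check first: "After investigators confirm and verify the inclusion and exclusion criteria, eligible subjects will be randomly assigned".

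In Protocol 3.0 the labels differ. For the test dressing: "Do not use at catheter insertion sites with dermatitis, burns, lesions or tattoos". For the control: "There are no known contraindications", although a warning follows against use on infected catheter sites.

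Protocol 19.3 and SAP 5.1 invoke intention to treat, but limit the FAS to "all subjects who are involved in the trial randomly and have used the trial product".

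**The concern.** Two things that should be fixed before allocation can be settled after it.

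- **Baseline skin records.** In the listed order, staff who know the arm score erythema, edema and itch and record whether skin infection is present. SAP 6.2.2 and 6.4 compare these records between arms, and SAP 6.3.1 adds baseline skin infection to the mixed model for colonisation.
- **Membership of the primary analysis set.** The catheter is already in place at Visit 1, and gauze or a hemostatic pad may have been applied. A lesion might first be noticed at the scored assessment. If a dressing is then withheld, the subject drops out of the FAS. The worst-case rule in SAP 7.3 does not reach that subject, because it fills missing endpoints only for subjects in the set. Subjects with damaged skin plausibly colonise more, so unequal loss would bias the comparison in favour of the arm that loses them.

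**Working it through.** **1. What the listed order implies for baseline.** Step 3 comes after step 2 (arm known) and before step 4 (treatment). A score taken at step 3 therefore meets the SAP definition of baseline while being taken with the allocation known. This needs no numerical assumption, only that the steps are done as listed.

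**2. Where those records are used.**
- SAP 6.2.2: insertion-site skin at baseline is compared between arms.
- SAP 6.3.1: the primary comparison is an unadjusted chi-square or Fisher test. An additional mixed model carries "insertion site, skin infection of baseline insertion site, and their interaction as random effects".
- SAP 6.4: skin findings at baseline and at the last visit are each compared between arms. No change-from-baseline analysis is specified for skin.

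**3. What a lesion found at step 3 means.** EC-8 names all four conditions in the test label's contraindication (dermatitis, burns, lesions, tattoos). The finding is thus a missed eligibility failure in either arm. Protocol 16.0 restricts devices to eligible subjects, again in either arm. What differs is the label: for a non-infectious lesion only the test product is contraindicated. The documents do not say how a lesion first noticed after allocation is handled, for treatment or for analysis.

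**4. The plan's own figure.** Inputs from Protocol 19.2: control rate p1 = 18.7%, a 50% reduction to p2 = 9.35% (difference 9.35 points), 80% power, two-sided 5%. With p̄ = (p1 + p2)/2,

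n = [z(1−α/2)·√(2p̄(1−p̄)) + z(0.80)·√(p1(1−p1) + p2(1−p2))]² / (p1 − p2)²

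gives 216 per group at α = 0.05 and 219 at the SAP's final α of 0.048, close to the stated 220. With a continuity correction it gives 237 and 239. Nothing below depends on this difference.

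**5. Size of the FAS effect.** Assume no true effect, an overall rate of 18.7%, a share f of subjects with a missed lesion, and colonisation rate r among them. Assume also that all such test subjects and no such control subjects leave the FAS. The spurious difference is

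0.187 − (0.187 − f·r)/(1 − f).

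| f (per 220) | r | Calculation | Difference, points |
|---|---|---|---|
| 3% (about 7) | 30% | 0.187 − 0.178/0.97 | 0.35 |
| 3% | 40% | 0.187 − 0.175/0.97 | 0.66 |
| 5% (11) | 30% | 0.187 − 0.172/0.95 | 0.59 |
| 5% | 40% | 0.187 − 0.167/0.95 | 1.12 |

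The standard error of the difference is √(2 × 0.187 × 0.813/220) = 3.7 points, so these biases are about 0.1 to 0.3 of a standard error.

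**6. Effect on false positives.** Let damaged skin carry relative risk RR. The rate in the remaining test subjects is then 0.187/(1 − f + f·RR). With d the resulting difference, s0 the pooled and s1 the unpooled standard error, 220 controls and 220(1 − f) test subjects, the chance of a result favouring test is Φ[(d − z·s0)/s1] at two-sided 0.048. Without loss it is 2.4%.

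| f | RR | d, points | False positives favouring test |
|---|---|---|---|
| 1% | 2 | 0.19 | 2.7% |
| 2% | 2 | 0.37 | 3.0% |
| 5% | 2 | 0.89 | 4.1% |
| 10% | 2 | 1.70 | 6.3% |
| 10% | 3 | 3.12 | 12.7% |

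If the skin is fully screened before allocation, f is close to zero and so is the bias.

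**The case against.** A reader might infer that a lesion found at step 3 bars only the test dressing, so that damaged-skin patients leave the FAS from the test arm alone. The documents do not support this. IC-5, EC-2 and EC-8 exclude such skin in both arms. Step 1, Protocol 4.1.2 and SAP 3.3 all put verification before assignment. Protocol 16.0 limits devices to eligible subjects regardless of arm, Protocol 12.1 makes an eligibility deviation reportable within 24 hours in either arm, and the control label warns against infected sites. Test-only loss needs a lesion missed at step 1, the test dressing withheld on label grounds, and the control dressing applied anyway. No section says this would happen. A subject with a second catheter might be dressed at that site and stay in the FAS.

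A reader might also infer that allocation-aware baseline records affect the primary test. They do not: that test is unadjusted.

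Other objections carry weight:

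- The Visit 1 list is not declared a strict sequence. The follow-up list in 10.2.3 puts the dressing change before the skin assessment, which suggests an inventory.
- The centre's routine dressing is transparent, so many sites may be visible at step 1.
- SAP 6.2.1 tabulates randomised subjects who did not use the product, so an imbalance would show.
- Last-visit skin scores are open-label whatever the order.

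These points reduce the concern but do not remove it. No text says the skin is scored before allocation or what follows a late finding, and tabulating lost subjects does not return them to the primary analysis.

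**Conclusion.** The point holds in a limited form. As listed, baseline skin records are made with the arm known; they feed between-arm skin comparisons and a supplementary model, not the primary test. Separately, the FAS condition lets a randomised subject leave the primary analysis set after allocation is known. Because the test label's contraindication is wider, that loss could be unequal, but unequal loss is a residual risk and not something the plan prescribes.

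Under the assumed inputs (3-5% missed lesions, 30-40% colonisation, loss from the test arm only) the bias is 0.35 to 1.12 points towards the test dressing. It becomes material only if missed lesions are considerably more common or carry a much higher risk. The documents give neither the lesion rate nor its colonisation risk. The change is worth making because it is cheap and removes both routes, not because a large bias has been shown.

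**What to change.** 1. In Protocol 10.2.2 and Table 10.3-1, place the skin assessment before randomisation, with the scores and the IC-5, EC-2 and EC-8 confirmation entered in the EDC before the online randomisation call.
2. In SAP 6.1, define baseline for skin variables as the last value before randomisation.
3. In Protocol 19.3 and SAP 5.1, define the FAS as all randomised subjects analysed as randomised, or prespecify that analysis alongside the current set. State that a subject found ineligible after allocation is treated identically in both arms for analysis.
4. Reconcile the device labels in Protocol 3.0 with the enrolment criteria and Protocol 16.0 on what happens when a lesion is noticed after allocation. The clinical rule itself is for the sponsor and investigator.

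**Cost.** Two steps change order and a few sentences are added. The randomisation call falls between the site inspection and the new dressing. Undressed subjects stay in the analysis, so their tip and skin cultures should still be collected. If none were cultured, SAP 7.3 would count them all as positive. With f = 5% and RR = 2 in the test arm only, the test rate would be 0.95 × 17.81% + 5% = 21.9%, which is 3.2 points above 18.7%. The unfilled result that SAP 7.3 already requires should be reported beside it.
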